4.3.3 Lactation

It is unknown whether sintilimab is secreted in breast milk. Considering that many

drugs are present in breast milk, sintilimab may have potential toxicity to infants. Women who are breastfeeding are not eligible for this study.

4.4 Criteria for Subject Discontinuation of Treatment/Withdrawal from the Study

4.4.1 Discontinuation of Study Treatment

Discontinuation of study treatment does not mean withdrawal from the study. Since certain clinical event data after discontinuation of treatment may be very important for the study, this information must be collected up to the subject's last scheduled visit, even if the subject has already stopped treatment.

Subjects may discontinue treatment at any time for any reason, or the researcher may decide whether to discontinue their treatment when any adverse event occurs. In addition, if the subject is not suitable for treatment, violates the study protocol, or for management and/or other safety reasons, the researcher or sponsor may discontinue the subject's treatment.

For any of the following reasons, the subject must discontinue treatment but can continue to be monitored in the study:

- The subject or the subject's legal representative requests to discontinue treatment.
- An adverse event occurs that requires treatment to be stopped as stipulated in the protocol (refer to Section 5.2).
- Another malignant tumor requiring active treatment occurs.
- A concurrent disease occurs that prevents further treatment.
- The researcher decides to withdraw the subject from the study.
- The subject's serum pregnancy test result is positive.
- The subject has poor compliance.
- The researcher and/or the sponsor believes that continuing to administer the study drug will place the subject at unnecessary risk based on the subject's disease condition or personal situation.
- Completion of 2 years of sintilimab treatment.

For subjects who have discontinued treatment but continue to be visited in the study, all visits and procedures listed in the study flowchart should be completed.

4.4.2 Withdrawal from the Study

If the subject or the subject's legal representative withdraws the informed consent to participate in the study, the subject must withdraw from the study. If the subject withdraws from the study, they will no longer receive treatment or scheduled visits. With the subject's consent, the subject can receive survival follow-up after withdrawing from the study. If the subject is lost to follow-up, they must withdraw from the study.

4.4.3 Clinical Criteria for Early Termination of the Study

The study will be prematurely terminated if the following criteria are met:

- The quality and quantity of data recorded are inaccurate or incomplete.
- Compliance with the study protocol and regulatory requirements is poor.

The incidence or severity of adverse drug reactions in this study or other studies suggests potential harm to the health of subjects. If the sponsor decides to no longer provide the study drug, adequate notice will be given to allow for appropriate adjustments to the subject's treatment.

5 Study Medication and Other Treatments

For all other study treatment cycles, the medication may be administered within 3 days before or after the first day of the planned weekly cycle at the discretion of the investigator for management reasons.

5.1 Use of Study Medication

The study medications in this trial are Sintilimab, Etoposide, Carboplatin, or Cisplatin (see Table 3). Other medications used during the study are considered non-study medications. Treatment plan: Sintilimab in combination with chemotherapy (Carboplatin/Cisplatin + Etoposide) for 4 or 6 cycles, followed by maintenance therapy with Sintilimab until disease progression, death, intolerable toxicity, withdrawal of informed consent, initiation of new antineoplastic treatment, or termination for other reasons specified in the protocol (whichever occurs first); eligible subjects may continue to use Sintilimab after the first disease progression (see Section 5.1.2); after resistance to immunotherapy, the investigator will determine and provide different treatment plans according to different resistance patterns, such as local treatment + immunotherapy.

5.1.1 Administration of Sintilimab

Sintilimab's main active ingredient is a recombinant humanized anti-programmed cell death receptor-1 monoclonal antibody with a concentration of 10 mg/mL. The product is a clear, colorless liquid, free of foreign matter, flocculent matter, and precipitate. Excipients include 140 mmol/L Mannitol, 25 mmol/L Histidine, 20 mmol/L Sodium Citrate Dihydrate, 50 mmol/L Sodium Chloride, 0.02 mmol/L Disodium Edetate (Sodium Ethylene Diamine Tetraacetate), 0.2 mg/mL Polysorbate 80, pH 6.0.

The minimum packaging unit of Sintilimab is a box, which contains 2 vials of Sintilimab (IBI308) injection liquid packed in a vial. The box is labeled with the drug name, dosage form, specifications, drug code, batch number, expiration date, storage conditions, and sponsor information. The labels on the vials and the box have the same information, but the vial labels do not have information on dosage form, precautions, and usage and

administration. All box and vial labels are markedFor Clinical Study Use Only. Sintilimab should be stored in the dark at 2~8°C, with a shelf life of 24 months.

If the injection shows turbidity, precipitation, or other quality issues, it should be immediately sealed and the sponsor notified.

The preparation and infusion process of Sintilimab is as follows:

- 1. Completely withdraw the injection liquid from 2 vials of Sintilimab and add it to a 100mL 0.9% (weight/volume) Sodium Chloride sterile saline intravenous infusion bag, and record the start time of preparation.
- 2. Gently invert the infusion bag to mix, ensuring the uniformity of the medication in the infusion bag, avoiding vigorous agitation to produce foam. If a large amount of foam is produced, the medication should be left to stand until the foam dissipates.
- 3. Administer the medication through an inline filter with a pore size of 0.2~1.2µm (the recommended infusion time is controlled within 30-60 minutes), and record the start and end times of the administration. Precautions: Confirm that the Sintilimab injection is transparent and free from turbidity, precipitation, or other quality issues before preparation; Ensure that the time from the first puncture and extraction of the Sintilimab injection to the end of the administration does not exceed 24 hours (the prepared medication should be stored under refrigeration at 2~8°C); Avoid mixing with other medications; Avoid intravenous bolus injection.

5.1.2 Use of Chemotherapy Medications

The standard chemotherapy drugs used in combination are prepared according to the descriptions in the approved product instructions, and the selected doses are as follows:

- Etoposide: 100mg/m² d1-3/g3w
- Cisplatin: 75mg/ m² d1/q3w
- Carboplatin: AUC 5 (calculated using the Calvert formula) d1/q3w, the dose of Carboplatin must not exceed 750mg.

Calvert Formula:

Total dose (mg) = (Target AUC) \times (CrCl + 25)

The estimated CrCl used in the Calvert formula must not exceed 125ml/min.

Maximum Carboplatin dose (mg) = Target AUC 5 (mg·min/ml) × $(125 + 25) = 5 \times 150$ ml/min = 750mg.

To prevent the nephrotoxicity of Cisplatin, adequate hydration is required: Hydration for 3 days is needed when using Cisplatin, along with potassium chloride, mannitol, and furosemide (Lasix), to maintain a daily urine volume of 2000-3000ml. Cisplatin is a highly emetogenic chemotherapeutic drug; it is recommended to use 5-HT3 receptor antagonists,

dexamethasone (or other glucocorticoids), dopamine receptor blockers (metoclopramide), antihistamines (such as diphenhydramine, benzhexol, etc.), and under conditionally, NK-1 receptor antagonists (aprepitant) to prevent chemotherapy-related vomiting.

Table 3 Study Treatment Medications

Drug	Dose/Amount	Administration	Method of	Treatment
		Frequency	Administration	Course/Cycle
Sintilimab	200mg	Q3W	Intravenous	Weekly on day
			infusion	1 of every 21-
				day cycle, up to
				2 years
Carboplatin	AUC 5	Q3W	Intravenous	Weekly on day
			infusion	1 of every 21-
				day cycle,
				maximum of 6
				cycles
Cisplatin	75mg/m ²	Q3W	Intravenous	Weekly on day
			infusion	1 of every 21-
				day cycle,
				maximum of 6
				cycles
Etoposide	100mg/m ²	Q3W	Intravenous	Weekly on day
			infusion	1 of every 21-
				day cycle,
				maximum of 6
				cycles

^{1.} Sintilimab should be administered before the chemotherapy drugs.

^{2.} If the subject's weight fluctuates by less than 10% from the baseline (the first dose of study treatment day), the baseline weight is used to calculate the body surface area (BSA), and the dosage of chemotherapy drugs is calculated accordingly. Conversely, the actual weight on the planned dosing day is used to calculate the chemotherapy drug dosage. The protocol allows a maximum BSA of 2.0 m $^{\circ}$ 2. For subjects with BSA > 2.0 m $^{\circ}$ 2, the research center staff will calculate based on a BSA of 2.0 m $^{\circ}$ 2. For convenience in dosing, the protocol permits a $\pm 5\%$ deviation from the calculated total dose for each infusion.

5.2 Dose Adjustments

5.2.1 Dose Adjustments for Sintilimab

- The dose of Sintilimab is not to be adjusted throughout the study. The principles for withholding and permanently discontinuing Sintilimab are outlined in Table 4. If an administration delay occurs during a 3-week cycle of Sintilimab treatment, all future dosing dates will be postponed to ensure that the dosing intervals between cycles of Sintilimab treatment are within 21 ± 3 days. Sintilimab-related adverse events are typically immune-related AEs. For pauses in administration due to immune-related AEs, based on the type and severity of the AE, corticosteroid treatment can be administered to alleviate to grade 1 or 0, and then the corticosteroids can be tapered over more than 4 weeks, after which the administration can be resumed.

Table 4: Dose Adjustment Scheme for Sintilimab-Related Immune Adverse Events

Immune-Related Adverse	Severity	Dose Adjustment
Events		
	Grade 2	Hold treatment ^a
Pneumonia	Recurrent Grade 2, Grade	Permanent discontinuation
	3 or 4	
	Grade 2 or 3 Diarrhea or	Hold treatment ^a
Diarrhea/Enterocolitis	Enterocolitis	
Diairriea/Enterocollis	Grade 4 Diarrhea or	Permanent discontinuation
	Enterocolitis	
Dermatitis	Grade 3 Dermatitis	Hold treatment ^a
Demanus	Grade 4 Dermatitis	Permanent discontinuation
	For subjects with normal	Hold treatment ^a
	baseline ALT, AST, or TBIL,	
	Grade 2 elevation of AST,	
	ALT, or TBIL; For subjects	
	with baseline AST, ALT, or	
Hepatitis	TBIL > ULN, an increase of	
riepatitis	AST, ALT, or TBIL \geq 50%	
	(meeting Grade 2	
	requirements) and duration	
	< 7 days	
	For subjects with baseline	Permanent discontinuation
	ALT, AST, or TBIL within	

	normal limits, Grade 3 or	
	Grade 4 elevation of AST,	
	ALT, or TBIL; for subjects	
	with baseline AST, ALT, or	
	TBIL > ULN (Upper Limit	
	of Normal), an increase in	
	AST, ALT, or TBIL by ≥50%	
	(meeting the criteria for	
	Grade 3 or Grade 4) and	
	duration ≥7 days	
	Grade 2	Hold treatment
pituitary inflammation	Grade 3 or Grade 4	Hold treatment or
		Permanent discontinuation
adrenal insufficiency	Grade 2	Hold treatment
	Grade 3 or Grade 4	Hold treatment or
		Permanent discontinuation
hyperthyroidism	Grade 3 or Grade 4	Hold treatment or
		Permanent discontinuation
hypothyroidism	Grade 2-4	Continue treatment
Type 1 diabete	Grade 3 hyperglycemia	Hold treatment
	Grade 4 hyperglycemia	Hold treatment or
		Permanent discontinuation
renal insufficiency	Grade 2 or Grade 3	Hold treatment ^a
	creatinine elevation	
	Grade 4 creatinine	Permanent discontinuation
	elevation	
neurotoxicity	Grade 2	Hold treatment ^a
	Grade 3 or Grade 4	Permanent discontinuation
	intolerable/persistent	Hold treatment ^a
	Grade 2 AE	
other immune-related AEs	Grade 3 AE	Hold treatment or
(Adverse Events)		Permanent discontinuation
	Grade 4 AE or recurrent	Permanent discontinuation
	Grade 3 AE	
 		

a: Treatment can be resumed once symptoms improve to Grade 0-1 or baseline levels.

b: Pituitary inflammation, adrenal insufficiency, hypothyroidism/thyroid dysfunction, and Type 1 diabetes can be reinitiated if adequately controlled and only physiological hormone replacement therapy is required.

c: For abnormal laboratory test results, the decision to hold or permanently terminate treatment should be based on accompanying clinical symptoms/signs and the clinical judgment of the investigator.

The maximum duration for holding Sintilimab treatment is 12 weeks. If the subject cannot recover to a state where Sintilimab can be reused within 12 weeks, the subject will permanently discontinue Sintilimab and enter the follow-up phase. Exceptions include the following two situations:

- If the use of glucocorticoids for treating irAE (immune-related adverse events) causes the hold of Sintilimab to exceed 12 weeks. In this case, it is necessary to discuss with the sponsor's medical manager to decide whether to continue. The imaging assessments for efficacy evaluation should proceed as planned without being affected by the suspension of the medication.
- Continuation of Sintilimab Treatment: In cases where the treatment is paused due to adverse events (AEs) not related to Sintilimab, the imaging assessments for efficacy evaluation should proceed as planned without being affected by the suspension of the medication.

5.2.2 Management of Sintilimab-Related Infusion Reactions

Sintilimab may cause severe or life-threatening infusion reactions, including severe hypersensitivity or allergic reactions. Signs and symptoms typically appear during or shortly after the infusion and can usually be completely resolved within 24 hours after the completion of the infusion. The management guidelines for infusion reactions related to Sintilimab are presented in Table 5.

Table 5: Management Guidelines for Sintilimab Infusion Reactions

NCI CTCAE Grade	Treatment	Premedication for
		Subsequent Dosing
1	According to the medical	No specific premedication
Mild reaction; no	indications of the patient,	required.
interruption of infusion is	monitor vital signs until the	
needed; no intervention	investigator deems the	
required.	subject's condition stable.	
2	Stop the infusion and	The subject may receive
Treatment or interruption of	monitor symptoms. Other	the following premedication

infusion may be necessary, but symptomatic treatment (such as antihistamines, nonsteroidal antiinflammatory drugs [NSAIDs], analgesics, intravenous fluid replacement) should be initiated promptly and a response is expected within ≤24 hours; prophylactic medication may required for up to 24 hours.

appropriate medications may include but are not limited to: intravenous fluids, antihistamines, NSAIDs, acetaminophen, analgesics.

According to the medical indications of the patient, monitor vital signs until the investigator deems the subject's condition stable.

If symptoms resolve within one hour after stopping the infusion, the infusion may be resumed at 50% of the original infusion rate (for example, from 100 mL/hr to 50 mL/hr). Otherwise, the medication should be suspended until symptoms resolve, and the subject should receive premedication before the next scheduled dosing. For subjects who still experience grade 2 toxicity after adequate premedication, further study drug treatment should be permanently discontinued.

1.5 hours (±30 minutes) before the infusion of Sintilimab:

Oral diphenhydramine 50 mg (or an equivalent dose of an antihistamine).

Oral acetaminophen 500-1000 mg (or an equivalent dose of an antipyretic).

Grade 3 or 4 Reactions:

Grade 3:

Stop the infusion.

Other appropriate

No further dosing.

Prolonged duration (i.e., failure to respond quickly after symptomatic treatment and/or brief interruption of infusion); symptoms recur after initial improvement; hospitalization required due to other clinical sequelae (such as renal impairment, pulmonary infiltration).

Grade 4:

Life-threatening; requiring pressor agents or ventilatory support.

medications may include but are not limited to:

- Epinephrine
- Intravenous fluids
- Antihistamines
- Nonsteroidal antiinflammatory drugs (NSAIDs)
- Acetaminophen
- Analgesics
- Oxygen
- Pressor agents
- Corticosteroids

Closely monitor the patient's vital signs according medical to indications until the investigator deems the subject's condition stable. Hospitalization may be required.

In the event of an allergic reaction, administer epinephrine immediately.

The subject should permanently discontinue further study drug treatment.

Appropriate emergency equipment should be available in the ward, and a physician should be readily accessible during the administration period. For further information, please refer to the Common Terminology Criteria for Adverse Events (CTCAE) version 5(http://ctep.cancer.gov).

5.2.3 Dose Adjustment of Chemotherapy Drugs:

If the investigator confirms that the toxic reaction is mainly caused by a single chemotherapy drug, a reduction in the dose of that single drug is acceptable; if it is not possible to clearly attribute the toxic reaction to two or more drugs, a reduction in all drugs considered relevant may be made simultaneously. If the administration of chemotherapy is delayed during a treatment cycle of every 3 weeks, all future dosing dates will be postponed to ensure that the dosing interval between chemotherapy cycles is 21±3 days. The chemotherapy cycle and the Sintilimab cycle should be synchronized as much as possible by adjusting the allowed window period. The maximum allowed period of discontinuation for chemotherapy drugs is 6 weeks from the last chemotherapy interval; if the requirements for chemotherapy administration cannot be met after more than 6 weeks, the chemotherapy should be permanently discontinued.

The following are the different dose levels for chemotherapy drugs. If a further dose reduction is required after reducing by two dose levels, discontinue the chemotherapy drug.

Table 6: Dose Adjustment Levels for Chemotherapy Drugs

	Original	One Dose Level	Two Dose Levels
	Dose	Reduction	Reduction
Etoposide	100mg/m ²	75 mg/m ²	50 mg/m ²
Cisplatin	75mg/m ²	56mg/m ²	38mg/m ²
Carboplatin	AUC 5,	AUC 3.75, maximum dose	AUC 2.5, maximum dose
	maximum	562.5mg	375mg
	dose, 750mg		

Table 7: Hematologic Toxicity Adjustments

Platelets	Neutrophils	Dose Adjustment According to	
		Table 6	
≥50×10^9/L	≥0.5×10^9/L	Original dose	
and			
≥50×10^9/L	<0.5×10^9/L	Reduce one dose level	
and			
<50×10^9/L ,	any condition	Reduce one dose level	
no bleeding			
and			
<50×10^9/L,	and any condition	Reduce two dose levels	

with bleeding		
Any condition	<1×10^9/L with fever ≥38.5°C	Reduce one dose level
and		

Table 8: Non-hematologic Toxicity

Adverse Event	CTCAE Grade	Cisplatin	Carboplatin
Nausea or Vomiting	Grade 3 or 4	Original dose	Original dose
Diarrhea	Grade 3 or 4	Reduce one dose	Original dose
		level	
Neuropathy	Grade 2	Reduce two dose	Original dose
		levels	
	Grade 3 or 4	Discontinue	Reduce one dose
		treatment	level
Transaminase	Grade 3	Reduce one dose	Reduce one dose
Elevation		level	level
	Grade 4	Discontinue	Discontinue
		treatment	treatment
Other Non-	Grade 3 or 4	Reduce one dose	Reduce one dose
hematologic Toxicity		level	level

Etoposide Dose Adjustment

Dose adjustments and delays are permitted. Adjustments are based on the product information and clinical guidelines, with recommended adjustments as shown in Table 9. If the investigator, considering the benefit/risk ratio of the subject, believes that they cannot follow the operations listed in the table or encounters a situation not listed in the table, and must suspend or resume etoposide, they should discuss and decide with the sponsor's investigator.

Creatinine Clearance (CrCl): CrCl is calculated using the Cockcroft-Gault formula based on the standard body weight (Appendix 2). Before the first administration of chemotherapy drugs, CrCl must be ≥50mL/min.

Table 9: Etoposide Dose Adjustment

Creatinine Clearance	Etoposide Dose
>50	100%

15-50	75% of the original dose

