screening phase should undergo a 24-hour urine protein quantification. Conducted within 7 days before the first dosing of the study drug in the screening phase, within 3 days before the dosing of the study drug at the beginning of the second cycle, and during the safety follow-up.

- 7. Women of childbearing age will undergo urine or serum pregnancy tests within 3 days before the first dosing in the screening phase and during the safety follow-up. If the urine pregnancy test result cannot be confirmed as negative, a serum pregnancy test will be conducted, and the serum pregnancy test result will prevail.
- 8. Thyroid function tests are conducted within 28 days before the first dosing, within 3 days before the dosing of the study drug at the beginning of the second cycle, and during the safety follow-up. In the screening phase, T3/FT3, FT4, and TSH are checked; from the second cycle, only TSH is checked, and if abnormal, other thyroid function indicators may be considered. During the study treatment process, it is not necessary to wait for the results of this test before proceeding with the study drug administration.
- 9. Include HIV and HCV antibody tests, as well as hepatitis B panel tests (HBsAg, HBsAb, HBcAb, HBeAg, HBeAb), which must be completed within 28 days before the first dosing. 10. AE and laboratory test safety assessments will be conducted according to CTCAE v5.0. The definition, recording, relatedness judgment, severity judgment, reporting timelines, and management of AEs and SAEs refer to the description in Section 8 of the protocol.
- 11. The quality of life questionnaire includes EORTC QLQ-C30 (V3.0 Chinese version), which is assessed on the day of the first dosing (before dosing), at each imaging assessment, and during safety follow-up. If an unplanned imaging assessment is conducted, the quality of life questionnaire should also be administered concurrently.

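### Table 7 gives two different chemotherapy doses in two situations of febrile neutropenia and does not say which row governs

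*Protocol*

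**What the plan says.** Section 5.2.3 of the protocol defines dose levels in Table 6 and assigns haematologic toxicity to those levels in Table 7. The five rows of Table 7, with counts in ×10^9/L, are:

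1. Platelets ≥50 and neutrophils ≥0.5: "≥50×10^9/L ≥0.5×10^9/L Original dose". Fever is not mentioned.
2. Platelets ≥50 and neutrophils <0.5: one level down.
3. Platelets <50 without bleeding, any neutrophil count: one level down.
4. Platelets <50 with bleeding: "and any condition Reduce two dose levels".
5. Any platelet count, neutrophils "<1×10^9/L with fever ≥38.5°C": one level down.

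The text of 5.2.3 covers neighbouring matters. If toxicity is attributed to one drug, "a reduction in the dose of that single drug is acceptable". On the limit to reductions it says: "If a further dose reduction is required after reducing by two dose levels, discontinue the chemotherapy drug". On delays it says: "if the requirements for chemotherapy administration cannot be met after more than 6 weeks, the chemotherapy should be permanently discontinued". The etoposide paragraph refers some decisions to a discussion, for investigators who "must suspend or resume etoposide, they should discuss and decide with the" sponsor's investigator. None of these sentences ranks the rows of Table 7, and neither the table nor the section says which blood counts the thresholds refer to.

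**The concern.** A dose-modification table should return one dose for each patient. Row 1 does not exclude fever, and row 5 does not exclude bleeding with low platelets, so some patients meet two rows that carry different instructions. The attribution rule decides which drug is reduced. The number of levels is what Table 7 is there to fix, and in these cases it does not fix it.

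Two things are at stake. One is safety: a literal reading of row 1 repeats full-dose chemotherapy in a patient who has just had febrile neutropenia. The other is consistency: two investigators following the same table could give the same patient different doses.

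**Working it through.** **Inputs.** The row conditions come from Table 7 and the dose levels from Table 6, both in section 5.2.3. The protocol states no summary figure to reproduce, but the Table 6 levels can be checked. They are 75% and 50% of the original dose:

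- Etoposide: 100 × 0.75 = 75 and 100 × 0.5 = 50 mg/m².
- Cisplatin: 75 × 0.75 = 56.25 and 75 × 0.5 = 37.5 mg/m², printed as 56 and 38.
- Carboplatin: 5 × 0.75 = AUC 3.75 and 5 × 0.5 = AUC 2.5.

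**Enumeration.** Cross platelets (≥50, <50), bleeding (yes, no), neutrophils (≥1.0, 0.5 to <1.0, <0.5) and fever ≥38.5°C (yes, no): 2 × 2 × 3 × 2 = 24 combinations. Each meets at least one row, so the table has no gaps. Row 5 applies whenever neutrophils are <1.0 with fever, which is 2 × 2 × 2 = 8 combinations. In each of these one other row also applies:

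| Situation (all with fever) | Other row | Other row's instruction | Row 5 | Result |
|---|---|---|---|---|
| Platelets ≥50, neutrophils 0.5 to <1.0 | 1 | original dose | one level | conflict (a) |
| Platelets ≥50, neutrophils <0.5 | 2 | one level | one level | agree |
| Platelets <50, no bleeding, neutrophils <1.0 | 3 | one level | one level | agree |
| Platelets <50, bleeding, neutrophils <1.0 | 4 | two levels | one level | conflict (b) |

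The conflicts take up 4 of the 24 combinations. They form two clinical situations, because (a) holds whether or not there is bleeding and (b) holds in both lower neutrophil bands.

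**Size of each conflict, starting from full dose.**

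| Drug | (a) row 1 vs row 5 | Ratio | (b) row 5 vs row 4 | Ratio |
|---|---|---|---|---|
| Cisplatin, mg/m² | 75 vs 56 | 75/56 = 1.34 | 56 vs 38 | 56/38 = 1.47 |
| Etoposide, mg/m² per day | 100 vs 75 | 100/75 = 1.33 | 75 vs 50 | 75/50 = 1.50 |
| Carboplatin, AUC | 5 vs 3.75 | 5/3.75 = 1.33 | 3.75 vs 2.5 | 3.75/2.5 = 1.50 |

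The higher of the two permitted doses exceeds the lower by 33 to 34% in (a) and by 47 to 50% in (b).

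**What row 5 contributes.** If the largest applicable reduction is used, row 5 changes the dose only in (a). Elsewhere rows 2, 3 and 4 already reduce by as much or more. If row 1 governed (a), row 5 would never add a reduction to what the other four rows require.

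**Which counts.** Table 1 schedules blood counts at screening, at cycle visits and at the safety visit, and none in mid-cycle. Its note 6 places one count "within 3 days before the dosing of the study drug at the beginning of the second cycle". Table 7 is not tied to that count or to any other.

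**The case against.** The strongest reply is that the table can be read sensibly as it stands. Row 5 has a purpose only if it overrides row 1, so (a) resolves towards the reduction. In (b), row 4 already covers every neutrophil count, and it would be perverse if adding fever halved the cut for a bleeding patient. If each row is taken as the reduction its own toxicity requires, with the larger one applied, both cases come out right. Case (b) also needs low platelets, bleeding, low neutrophils and fever together, and the protocol gives no rate for it. All of this stands as an account of the likely intent and as a reason to rate the point low. It does not supply the missing rule. The simplest alternative, treating row 5 as an exception to the other rows, gives the right answer in (a) and the wrong one in (b).

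Three stronger readings might be inferred, and the protocol does not support them:

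- **A patient already one level down must stop the drug under row 4.** That requires reductions to be counted from the current dose. The rule on a further reduction after two levels leans that way, but Table 7 refers to Table 6, whose columns are set against the original dose. Read so, row 4 places this patient at the second level and nothing stops. The protocol does not state which applies.
- **Table 7 authorises full dose on Day 1 at neutrophils of 0.5 and platelets of 50.** The table is titled as a toxicity adjustment, its rows describe events such as fever and bleeding, and 5.2.3 refers separately to requirements for giving chemotherapy. That no Day 1 minimum count is stated is an omission, and Table 7 does not contradict it.
- **The ambiguity affects the efficacy result.** Nothing in the protocol shows an effect on the 1-year PFS rate.

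**Conclusion.** The point holds as a contradiction between stated dosing rules. Table 7 gives different doses in exactly two situations, and section 5.2.3 has no rule of precedence. The difference is one dose level in each. This rests on reading the row conditions as printed; thresholds and actions are legible in every row, so the layout of the table does not create the overlap. The probable intent is that the more severe row applies, which makes this a minor safety and consistency point. The protocol gives no frequency for either situation, so the number of affected cycles cannot be estimated.

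**What to change.** Add one sentence under Table 7: *If more than one row applies, use the largest reduction.* Situation (a) then gives one level down (cisplatin 56 mg/m², etoposide 75 mg/m², carboplatin AUC 3.75), and (b) gives two levels down (38 mg/m², 50 mg/m², AUC 2.5). An equivalent change is to limit row 1 to patients without neutrophils <1.0 with fever, and to exclude row 4 cases from row 5.

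As a clarification, head the table as the lowest counts observed in the previous cycle, so that it is not taken as permission for full dose at Day 1 neutrophils of 0.5. Because Table 1 schedules no mid-cycle count, this will often rest on unscheduled tests, so the gain is partial.

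Both are text changes by amendment and add no visits or blood draws. The cost is a few more reduced cycles. While the amendment is open, the sponsor could also state whether reductions are cumulative, since that decides what row 4 means for a patient already reduced.
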